12.2.7 Summary of Baseline Characteristics and Demographics

Baseline characteristics will be assessed by the use of tables and/or graphs for each cohort separately. No statistical hypothesis tests will be performed on these characteristics. The number and percentage of subjects screened, randomized, the primary reasons for screening failure, and the primary reason for discontinuation will be displayed. Demographic variables (e.g., age, gender), baseline characteristics, primary and secondary diagnoses, and prior and concomitant therapies will be summarized by treatment either by descriptive statistics or categorical tables.

12.2.8 Compliance (Medication Adherence)

A day within the study will be considered an On-Therapy day if the subject receives the study medication infusion. The number of Days Should be on Therapy is the total number of days from the first day of study medication to the date of the last dose of study medication. For each subject, percent compliance will then be calculated using the following formula:

Percent Compliance =

(Number of Days Should be on Therapy/Number of Days on Therapy) x 100

Summary statistics will be provided on percent compliance by treatment group for the FAS population.

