5.1 Trial Treatments

The treatment to be used in this trial is outlined below. Each treatment cycle will be 6 weeks (42 days).

Table 2 Trial Treatment

Drug	Dose/ Potency	Dose Frequency	Route of Administration	Regimen/Treatment Period	Use
Pembrolizumab	200 mg	Q3W	IV infusion	Days 1 and 22 of each 6-week (42 day) cycle	Experimental

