5.2 Dose Selection/Modification

Dose Selection

The rationale for selection of doses to be used in this trial is provided in Section 2.3.2 – Background and Rationale.

Details on preparation and administration of pembrolizumab (MK-3475) are provided in the Pharmacy Manual.

Dose Modification

No dose reductions (in dose or frequency) are permitted. Only dose holds are permitted per protocol. Treatment may be held for up to 12 weeks (84 days) from last dose.

Adverse events (both non-serious and serious) associated with pembrolizumab exposure may represent an immunologic etiology. These adverse events may occur shortly after the first dose or several months after the last dose of treatment. Pembrolizumab must be withheld for drug-related toxicities (considered at least possibly related to study treatment) and severe or life-threatening AEs as per Table 3 below. If a participant experiences a toxicity unlikely or unrelated to treatment

with pembrolizumab, but may still warrant a hold or reduction of study drug for safety, discussion and writing approval by the Overall Principal Investigator and Study Sponsor, [name], is recommended but not required.

See Section 5.7 for supportive care guidelines, including use of corticosteroids.

Table 3 Dose Modification Guidelines for Drug-Related Adverse Events

Toxicity	Hold Treatment For Grade	Timing for Restarting Treatment	Treatment Discontinuation
Diarrhea/Colitis	2-3	Toxicity resolves to Grade 0-1.	Toxicity does not resolve within 12 weeks of last dose or inability to reduce corticosteroid to 10 mg or less of prednisone or equivalent per day within 12 weeks.
	4	Permanently discontinue	Permanently discontinue
AST, ALT, or Increased Bilirubin	2	Toxicity resolves to Grade 0-1	Toxicity does not resolve within 12 weeks of last dose.
	3-4	Permanently discontinue (see exception below) ¹	Permanently discontinue
Type 1 diabetes mellitus (if new onset) or Hyperglycemia	T1DM or 3-4	Hold pembrolizumab for new onset Type 1 diabetes mellitus or Grade 3-4 hyperglycemia associated with evidence of beta cell failure.	Resume pembrolizumab when patients are clinically and metabolically stable within 12 weeks of last dose.
Hypophysitis	2-4	Toxicity resolves to Grade 0-1. Therapy with pembrolizumab can be continued while endocrine replacement therapy is instituted	Toxicity does not resolve within 12 weeks of last dose or inability to reduce corticosteroid to 10 mg or less of prednisone or equivalent per day within 12 weeks.

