¹ For patients with liver metastasis who begin treatment with Grade 2 AST or ALT, if AST or ALT increases by greater than or equal to 50% relative to baseline and lasts for at least 1 week then patients should be discontinued.

² If symptoms resolve within one hour of stopping drug infusion, the infusion may be restarted at 50% of the original infusion rate (e.g., from 100 mL/hr to 50 mL/hr). Otherwise dosing will be held until symptoms resolve and the subject should be premedicated for the next scheduled dose; Refer to

Table – Infusion Treatment Guidelines for further management details.

³Patients with intolerable or persistent Grade 2 drug-related AE may hold study medication at physician discretion. Permanently discontinue study drug for persistent Grade 2 adverse reactions for which treatment with study drug has been held, that do not recover to Grade 0-1 within 12 weeks of the last dose.

Dosing interruptions are permitted in the case of medical / surgical events or logistical reasons not related to study therapy (e.g., elective surgery, unrelated medical events, patient vacation, and/or holidays). Subjects should be placed back on study therapy within 3 weeks of the scheduled interruption, unless otherwise discussed with the Sponsor. The reason for interruption should be documented in the patient's study record.

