- d. End of Tx: End of treatment assessments to be performed within 7 days after last drug administration or within 7 days after decision to end treatment. Assessments may continue for ongoing reportable adverse events.
- e. 30-Day Post Drug: A contact/visit is to be performed at 30 days ($+ 7$ days) after the last study drug is given. This may be performed via documented phone conversation with a study nurse or clinician or a clinic visit. All participants will be followed until resolution or stabilization of any serious or reportable adverse events occurring during treatment or starting within 30 days of last study drug.
- f. Active Follow Up: For participants who discontinue study treatment for reasons other than disease progression, every effort should be made to continue monitoring their disease status by radiologic imaging at a schedule developed by the treating investigator until (1) documented disease progression, (2) death or (3) the end of the study, whichever occurs first.
- g. Long Term Follow Up: participants will be followed every 3 months ($+/- 1$ month) via contact or medical record review until death for post-treatment therapies, reason for stopping those therapies and survival.
- h. Informed Consent: Must be obtained by MD attending. No study specific screening procedures may occur until after the informed consent process is complete. Informed Consent may be obtained within 28 days of registration.
- i. Background information/history: to include review of treatment history for GBM, any ongoing medical conditions and medical history pertaining to eligibility on study and involvement during study.
- j. Inclusion/exclusion criteria: source documentation providing investigator's confirmation that the participant had met all eligibility criteria must be available prior to registration.
- k. Vital signs: weight, heart rate, blood pressure, respiration rate, temperature. Vital signs must be performed prior to administration of treatment on treatment days. Height required only at screening and may be obtained within 1 year of registration.
- l. Neurologic Exam: to be completed by the investigator or qualified designee at screening, C1D1 and start of all subsequent cycles.
- m. Directed Physical Exam: to be completed as clinically indicated by the investigator or qualified designee.
- n. Performance Status: See Appendix A for KPS scale.

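### The percent-compliance formula in 12.2.8 is inverted and divides calendar days by infusion days: perfect 21-day dosing scores 1,100% at 2 doses and 1,878% at 9, and a missed middle dose raises the score

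*Combined protocol and SAP*

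**What the plan says.** Section 12.2.8 defines two counts. For the actual count, "A day within the study will be considered an On-Therapy day if the subject receives the study medication infusion". The expected count is the "total number of days from the first day of study medication to the date of the last dose of study medication". Percent compliance is then "Number of Days Should be on Therapy/Number of Days on Therapy) x 100". On reporting: "Summary statistics will be provided on percent compliance by treatment group for the FAS population".

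The dosing schedule is in Table 2 of section 5.1: "Days 1 and 22 of each 6-week (42 day) cycle", that is, one infusion every 21 days. Footnote x of the Study Calendar (section 9) adds, for Group A only, one infusion 14 ± 5 days before surgery. In both groups post-surgical dosing must start within 35 days of surgery.

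Section 5.2 expects gaps in dosing. For toxicity: "Treatment may be held for up to 12 weeks (84 days) from last dose". For other causes: "Dosing interruptions are permitted in the case of medical / surgical events or logistical reasons not related to study therapy".

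No other section redefines the compliance score, and the documents state no expected value for it.

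**The concern.** There are three separate defects.

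1. **Inversion.** Expected is divided by actual, so fewer infusions over the same span give a higher score.
2. **Mixed units.** Calendar days are divided by infusion days. With one infusion every 21 days, neither orientation gives 100% for a patient who received every dose (a single dose aside).
3. **Truncated span.** The expected count stops at the last dose actually given, so nothing omitted after it can count. Footnote d of the Study Calendar shows that treatment need not end at an infusion: "End of treatment assessments to be performed within 7 days after last drug administration or within 7 days after decision to end treatment". A scheduled infusion can therefore fall between the last dose and the decision.

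At stake is a table reported by treatment group under an adherence heading. Its values could not be read as adherence, and a difference between groups could reflect surgical scheduling.

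**Working it through.** The plan gives no compliance figure to reproduce, so the printed formula is applied to the printed schedule.

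**Inputs.** 21-day spacing (5.1). Group A's pre-surgical dose is at most 14 + 5 = 19 days before surgery and its first post-surgical dose at most 35 days after (section 9, footnote x), so the longest gap is 19 + 35 = 54 days. Section 12.2.8 does not say whether both end days count; inclusive counting is used below, with date differences as the alternative.

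**Group B, k doses, perfect adherence:** score = 100 x [1 + 21(k − 1)] / k. With date differences: 100 x 21(k − 1) / k.

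| Doses | Inclusive | Date differences | Ratio flipped (inclusive) |
|---|---|---|---|
| 1 | 1/1 = 100% | 0% | 100% |
| 2 | 22/2 = 1,100% | 21/2 = 1,050% | 2/22 = 9.1% |
| 5 | 85/5 = 1,700% | 84/5 = 1,680% | 5/85 = 5.9% |
| 9 | 169/9 = 1,878% | 168/9 = 1,867% | 9/169 = 5.3% |

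The only fully adherent patient who scores 100% is one who stopped after a single infusion, and only under inclusive counting.

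**Missed middle dose** (same first and last day, one infusion fewer):
- 4 of 5: 85/4 = 2,125%, up from 1,700%.
- 8 of 9: 169/8 = 2,113%, up from 1,878%.

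**Omitted final dose of 9:** 148/8 = 1,850%, exactly the score of a patient scheduled for 8 who received all 8.

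**Group A, perfect adherence,** first gap g, then 21-day spacing: score = 100 x [1 + g + 21(k − 2)] / k. Subtracting the Group B formula leaves 100 x (g − 21) / k percentage points.
- g = 54, k = 9: 202/9 = 2,244%, which is 367 points above Group B.
- g = 54, k = 2: 55/2 = 2,750%, which is 1,650 points above Group B.
- g = 35 (assumed: surgery 14 days after the dose, restart 21 days later), k = 9: 183/9 = 2,033%.
- g = 21: equal to Group B at every k.

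**Permitted hold.** Doses on days 1, 22, 106, 127 and 148 contain one 84-day interval and score 148/5 = 2,960%.

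**The case against.** The best reply is that this is a drafting slip that cannot mislead. A score of 1,100% would be questioned on first output, the drug is infused in clinic so dose dates are recorded, and no test uses the score. That stands as far as consequences go, and it is why the point is minor. It does not rescue the text. Flipping the ratio leaves 5% to 9% for perfect dosing, so whoever programmes the table would have to invent new definitions for both terms. Extent of Exposure (12.2.9) is no substitute: it counts cycles in which an infusion was received, so as worded a cycle with one of its two infusions counts the same as a complete one.

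Two stronger readings are tempting and are not supported.

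- A reader might infer that Groups A and B must show different scores under perfect adherence. They need not: a 21-day gap across surgery makes them equal, and the protocol does not fix that gap. They could differ, by an amount that depends on surgical timing.
- A reader might infer that every dose not given in a hold is non-adherence. Section 5.2 requires withholding for the listed drug-related toxicities. The documents also do not settle whether scheduled days keep running during a hold; section 7.1.6 speaks of lengthening intervals for toxicity. In the 84-day example, counting the skipped days 43, 64 and 85 gives 5/8 = 62.5%, while a shifted schedule gives 5/5 = 100%. A patient managed exactly per protocol should not be scored on an unstated convention.

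**Conclusion.** The formula is wrong as written, and this follows from the text of 12.2.8 alone. The exact percentages assume 21-day spacing and inclusive days; counting date differences changes the level slightly and the conclusion not at all. The same holds for the dosing window: moving the last dose by 3 days either way gives 950% to 1,250% at 2 doses and 1,844% to 1,911% at 9.

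Severity is minor. One descriptive table is affected. The primary comparisons, the power calculation, PFS6 and the safety summaries do not use the score, and nothing here suggests that any of them is biased.

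**What to change.** Replace the formula in 12.2.8 with:

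percent compliance = 100 x infusions received / (infusions received + infusions omitted)

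- **Omitted:** an infusion whose protocol-allowed window closed, on or before the date of removal from protocol therapy, without the infusion being given. The windows are those already in the protocol: ± 3 days for Days 1 and 22, 35 days after surgery for the first post-surgical infusion, and 14 ± 5 days before surgery for Group A's pre-surgical infusion.
- **Not omitted:** infusions withheld under holds or interruptions that section 5.2 permits. Report their number separately, and state whether scheduled days keep running during a hold, since that affects this count but not the score.

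The denominator is built from received plus omitted for a reason. Infusions scheduled before the decision to end treatment would be simpler, but if that decision falls on the day of the fifth on-time infusion the score is 5/4 = 125%, and on the day of a Group B patient's first infusion it is 1/0.

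Checks on the replacement:
- On-time dosing scores 100% at any surgical gap, and also when treatment ends on an infusion day: 5/(5 + 0).
- One missed dose of five scores 4/(4 + 1) = 80%, including a final dose whose window had closed.
- The 84-day hold example scores 5/5 = 100%, with the held infusions listed.
- The denominator is never zero, because the FAS requires at least one dose (12.2.5.1).

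The cost is a few sentences. Section 5.9 already requires the removal date and reason in the CRF. The reason for each infusion not given is also needed; section 5.2 requires the reason for an interruption in the patient's study record, and it may have to be taken from there, since the CRF fields are not shown. The opening of section 12 allows changes to non-confirmatory analyses to be listed in the Clinical Study Report.

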12.2.9 Extent of Exposure

Extent of Exposure for a subject is defined as number of cycles in which the subject receives the study medication infusion. Summary statistics will be provided on Extent of Exposure for APaT population.

13. PUBLICATION PLAN

This trial is intended for publication, even if terminated prematurely. Publication may include any or all of the following: posting of a synopsis online, abstract and/or presentation at a scientific conference, or publication of a full manuscript. The Sponsor will work with the authors to submit a manuscript describing trial results within 12 months after the last data become available, which may take up to several months after the last subject visit in some cases. The Overall Principal Investigator will post a synopsis of trial results for approved products on www.clinicaltrials.gov by 12 months after the last subject's last visit for the primary outcome, 12 months after the decision to discontinue development, or product marketing (dispensed, administered, delivered or promoted), whichever is later.

These timelines may be extended for products that are not yet marketed, if additional time is needed for analysis, to protect intellectual property, or to comply with confidentiality agreements with other parties. Authors of the primary results manuscript will be provided the complete results from the Clinical Study Report, subject to the confidentiality agreement. When a manuscript is submitted to a biomedical journal, the Sponsor's policy is to also include the protocol and statistical analysis plan to facilitate the peer and editorial review of the manuscript. If the manuscript is subsequently accepted for publication, the Sponsor will allow the journal, if it so desires, to post on its website the key sections of the protocol that are relevant to evaluating the trial, specifically those sections describing the trial objectives and hypotheses, the subject inclusion and exclusion criteria, the trial design and procedures, the efficacy and safety measures, the statistical analysis plan, and any amendments relating to those sections. The Sponsor reserves the right to redact proprietary information.

For multicenter trials, subsequent to the multicenter publication (or after public disclosure of the results online at www.clinicaltrials.gov if a multicenter manuscript is not planned), an investigator and his/her colleagues may publish their data independently. In most cases, publication of individual trial site data does not add value to complete multicenter results, due to statistical concerns. In rare cases, publication of single trial site data prior to the main paper may be of value. Limitations of single trial site observations in a multicenter trial should always be described in such a manuscript.

Authorship credit should be based on 1) substantial contributions to conception and design, or acquisition of data, or analysis and interpretation of data; 2) drafting the article or revising it critically for important intellectual content; and 3) final approval of the version to be published. Authors must meet conditions 1, 2 and 3. Significant contributions to trial execution may also be taken into account to determine authorship, provided that contributions have also been made to all three of the preceding authorship criteria. Although publication planning may begin before conducting the trial, final decisions on authorship and the order of authors' names will be made based on participation and actual contributions to the trial and writing, as discussed above. The first author is responsible for defending the integrity of the data, method(s) of data analysis and the scientific content of the manuscript.

The Sponsor must have the opportunity to review all proposed abstracts, manuscripts or presentations regarding this trial 45 days prior to submission for publication/presentation. Any information identified by the Sponsor as confidential must be deleted prior to submission; this confidentiality does not include efficacy and safety results. Sponsor review can be expedited to meet publication timelines.

REFERENCES

1. CBTRUS. *CBTRUS: 2010 Statistical Report: Primary Brain and Central Nervous System Tumors Diagnosed in the United States in 2004-2006*. 2010.

APPENDIX A KARNOFSKY PERFORMANCE STATUS

Grade	Description
100	Normal, no complaints; no evidence of disease
90	Able to carry on normal activity; minor signs or symptoms of disease.
80	Normal activity with effort; some signs or symptoms of disease.
70	Cares for self; unable to carry on normal activity or to do active work.
60	Requires occasional assistance, but is able to care for most of his personal needs.
50	Requires considerable assistance and frequent medical care.
40	Disabled; requires special care and assistance.
30	Severely disabled; hospital admission is indicated although death not imminent.
20	Very sick; hospital admission necessary; active supportive treatment necessary.
10	Moribund; fatal processes progressing rapidly.
0	Dead.

1.0 INTRODUCTION

The Dana-Farber/Harvard Cancer Center Multi-Center Data and Safety Monitoring Plan (DF/HCC DSMP) outlines the procedures for conducting a DF/HCC Multi-Center research protocol.

1.1 Purpose

To establish standards that will ensure that a Dana-Farber/Harvard Cancer Center Multi-Center protocol will comply with Federal Regulations, Health Insurance Portability and Accountability Act (HIPAA) requirements and applicable DF/HCC Standard Operating Procedures.

1.2 Multi-Center Data and Safety Monitoring Plan Definitions

DF/HCC Multi-Center Protocol: A research protocol in which one or more outside institutions are collaborating with Dana-Farber/Harvard Cancer Center where a DF/HCC investigator is the sponsor. DF/HCC includes Dana-Farber/Partners Cancer Care (DF/PCC) Network Clinical Trial Affiliates.

Lead Institution: Among the Dana-Farber/Harvard Cancer Center sites (DFCI, MGH, BIDMC, CHB, BWH), the Dana-Farber Cancer Institute will be the Lead Institution and will be responsible for the coordination, development, submission, and approval of a protocol as well as its subsequent amendments per the DFCI IRB and applicable regulatory guidelines (FDA, etc.). The Lead Institution is the home of the Overall PI.

DF/HCC Sponsor: The person sponsoring the submitted Multi-Center protocol who takes responsibility for initiation, management and conduct of the protocol at all research locations. The DF/HCC Sponsor has ultimate authority over the protocol and is responsible for the conduct of the study at DF/HCC and all Participating Institutions. For this protocol the DF/HCC Sponsor is the same person as the DF/HCC Overall Principal Investigator.

Participating Institution: An institution that desires to collaborate with DF/HCC and commits to accruing participants to the DF/HCC protocol. The Participating Institution acknowledges the DF/HCC Sponsor as having the ultimate authority and responsibility for the overall conduct of the study.

Coordinating Center: The entity that provides administrative support to the DF/HCC Sponsor in order that he/she may fulfill the responsibilities outlined in the protocol document and DSMP, and as specified in applicable regulatory guidelines. In general, the Lead Institution is the Coordinating Center for the DF/HCC Multi-Center Protocol.

DF/HCC Office of Data Quality: A group within DF/HCC responsible for registering human subjects for trials, ensuring high-quality standards are used for data collection and the ongoing management of clinical trials, auditing, and data and safety monitoring. ODQ also coordinates quality assurance efforts related to multi-center clinical research.

DF/HCC Clinical Trials Research Informatics Office (CTRIO): A group within DF/HCC responsible for providing comprehensive data management platform for managing clinical trial data.

